3.0 Inclusion and Exclusion Criteria*

Patients with gynecological cancer who are referred to receive treatment at Brigham and Women's Hospital (BWH) and/or Dana-Farber Cancer Institute (DFCI), and who will undergo routine clinical standard of care pelvic MRI, are eligible to participate in the study. Subjects with benign uterine fibroids referred to routine pelvic MRI at BWH will serve as controls.

Inclusion Criteria

- Participants with suspected or histologically confirmed diagnosis of primary or recurrent gynecological cancer including uterine endometrial, cervical, vaginal, vulvar, ovarian, and smooth-muscle tumors undergoing routine clinical standard of care pelvic MRI
- Control subjects with benign fibroids undergoing routine clinical standard of care pelvic MRI
- Age \geq 18 years
- ECOG performance status of \leq 2, based on treating physician's discretion (Appendix A)
- Ability to understand and the willingness to sign a written informed consent document

Exclusion Criteria

- Contraindication to MRI identified by the MR procedure screening form, such as a pacemaker, aneurysm clip, inner ear implant, neurostimulator, or other MR non-compatible device or implant
- Uncontrolled intercurrent illness including, but not limited to ongoing or active infection, symptomatic congestive heart failure, unstable angina pectoris, cardiac

arrhythmia, or psychiatric illness/social situations that would limit compliance with study requirements

- Adults unable to consent
- Non-english speaking subjects
- Pregnant women
- Prisoners

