sequences (QTI and MRF). Scanning time will be increased with 10–15 minutes which may cause discomfort to participants due to laying on the scanning table for a longer period of time.

Follow-up data including treatment outcome, tumor histology, clinical variables, laboratory results, medical images, and survival data, will be collected from the participant's electronic medical records. For survival data, the duration of follow-up is up to 4 years after participation and the MRI scan with new MRI methods.

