11.0 Data Management* and Confidentiality

11.1 Data analysis plan and statistical procedures

Primary endpoint of this study is to evaluate the feasibility of MRF and QTI in gynecological pelvic MRI. Feasibility will be assessed in two ways. First, the aspects of image quality such as artifacts, sharpness, and noise will be evaluated by two radiologists. Second, regions-of-interest (ROI) of the tumor and normal tissue (uterine normal endometrium, myometrium, cervical stroma, ovaries) will be recorded and ROI-based parameters from MRF (T1 and T2 relaxation values) and QTI (total mean kurtosis MK_T , microscopic anisotropy MK_A , isotropic heterogeneity MK_I , fractional anisotropy FA, microscopic fractional anisotropy μFA) will be compared between the tumor and normal tissue, and between different tumor histologies. One-way analysis of variance will be used to determine the statistical difference of each MRF and QTI value between the malignant tumors, benign fibroids, and normal tissue.

Secondary endpoint is to assess the predictive and prognostic value of MRF and QTI in gynecological malignancies. For this purpose, MRF and QTI parameters from gynecological malignancies will be compared with the treatment effect

assessed by clinical examination and/or cross-sectional follow-up imaging, and the participants' outcome by means of Kaplan-Meier method with log rank test, and Cox proportional-hazards model.

Variables that will be collected include the quantitative MRI parameters, demographic information (age, sex), clinical variables (diagnosis, tumor stage, histopathologic and molecular data, laboratory results, treatment, dates of diagnosis and treatments), follow-up images, and outcome data (recurrences, survival). An Excel database including MRI and clinical variables will be developed for the purposes of this study.

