23.0 Local Number of Subjects

Based on sample size calculation (see Section 11.2 Power Analysis), following number of participants will be included in this research study:

1. MRF for participants with gynecologic malignancy; n=27
2. MRF for participants with benign uterine fibroid; n=27
3. QTI for participants with gynecologic malignancy; n=27
4. QTI for participants with benign uterine fibroid; n=27

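### The outcome analyses in 11.1 do not separate primary from recurrent disease or require a pre-treatment scan, so an MRI parameter can look prognostic by marking disease status, and a post-treatment scan can serve as a predictor.

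*Combined protocol and SAP*

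**What the plan says.** **Who enters.** Section 3.0 of the combined protocol and SAP opens with "Patients with gynecological cancer who are referred to receive treatment at" the two institutions and who are having a routine pelvic MRI. The inclusion list then takes "Participants with suspected or histologically confirmed diagnosis of primary or recurrent gynecological cancer", across several tumour types. The exclusions begin with "Contraindication to MRI identified by the MR procedure screening form" and go on to uncontrolled illness, inability to consent, language, pregnancy and imprisonment. None concerns treatment already given or under way.

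**What is analysed.** Section 11.1 states that "MRF and QTI parameters from gynecological malignancies will be compared with the treatment effect", and also with the participants' "outcome by means of Kaplan-Meier method with log rank test, and Cox proportional-hazards model". It describes the aim as predictive and prognostic value. No stratum, covariate, subset or scan-to-treatment window is named.

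**What is collected.** Section 11.1 lists "tumor stage, histopathologic and molecular data, laboratory results, treatment, dates of diagnosis and treatments", among other variables. Whether the disease was primary or recurrent at the scan is not listed by name.

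**Clock and size.** For survival, section 9.0 says "the duration of follow-up is up to 4 years after participation and the MRI scan with new MRI methods". Section 23.0 gives "MRF for participants with gynecologic malignancy; n=27", and the same number for QTI.

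**The concern.** Two separate problems follow if 11.1 is carried out as written.

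1. **Confounding by disease status.** Recurrent tumours may differ from primary tumours in the MRI parameter and also in prognosis. If both hold, a parameter that says nothing about prognosis among primary cases, or among recurrent cases, will still be associated with survival when the two are analysed together.

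2. **Order in time.** A parameter measured after treatment began may partly reflect that treatment. It cannot then be read as a baseline predictor of the same treatment's effect. Section 1.0 itself lists telling residual tumour from treatment-related change as an intended use of these sequences, so the plan expects treatment to alter the signal.

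At stake is the secondary prognostic objective: a published association could be taken as evidence for a biomarker when it only restates something the clinician already knows.

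**Working it through.** **The plan's own figure.** Section 11.2 assumes a 5% difference on 78 ms, which is 3.9 ms, with SD 5 ms. The standardised difference is 3.9/5 = 0.78. By the normal approximation, n = 2 × (1.96 + 0.84)² / 0.78² ≈ 25.8, so 26 per group. The t-based version gives 26.8, so 27. The stated 27 reproduces, but it is sized for a comparison of mean T2. No figure is given for the outcome analysis.

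**Inputs for the confounding check**

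- From the documents: 27 malignant cases per sequence (23.0) and follow-up of up to 4 years from the scan (9.0). The check takes the full 4 years for everyone.
- Assumed: 4, 7 or 13 recurrent cases; hazard 0.12 per year in primary disease; recurrent-versus-primary hazard ratio (HR) of 2, 3 or 4; parameter shift of 0.4 or 0.78 SD in recurrent cases; no parameter effect within either group. The 0.78 borrows the size of the between-histology T2 assumption in 11.2. The plan states no primary-versus-recurrent difference.

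**Events implied.** Expected events = (27 − r)(1 − e^(−0.12×4)) + r(1 − e^(−0.12×4×HR)), with r recurrent cases.

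- r = 13, HR 2: 14 × 0.381 + 13 × 0.617 ≈ 13.4
- r = 13, HR 4: 14 × 0.381 + 13 × 0.853 ≈ 16.4
- r = 4, HR 2: 23 × 0.381 + 4 × 0.617 ≈ 11.2

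**Rejection rate of the unstratified Cox test at a nominal 5%** (2,000 simulated cohorts per cell, exponential times censored at 4 years; Monte Carlo error about 0.5 to 0.7 points)

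| Recurrent of 27 | Shift (SD) | HR 2 | HR 3 | HR 4 |
|---|---|---|---|---|
| 13 | 0.78 | 8% | 12% | 15% |
| 13 | 0.4 | 6.5% | 7.0% | 7.4% |
| 7 | 0.78 | 8.1% | 9.6% | 11.5% |
| 7 | 0.4 | 5.3% | 6.0% | 7.9% |
| 4 | 0.78 | 5.6% | 6.9% | 7.6% |

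Repeat runs of the first row gave 7.0% to 7.5% at HR 2, 11.6% to 11.7% at HR 3 and 14.6% to 17.0% at HR 4, so about 16% is a fair upper figure. In that row the spurious hazard ratio per SD of the parameter is about 1.12 to 1.25.

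**Controls.** With 13 recurrent cases, a 0.78 SD shift and HR 1, so that recurrence carries no prognosis, the unstratified test rejects in 5.1%. The excess therefore comes from combining groups with different prognosis. Stratified by disease status, the test rejects in about 5% to 7% over the settings examined.

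**A second set of assumptions** (30% to 50% recurrent, primary hazard 0.10 per year, shift 0.5 to 1.0 SD, HR 2 to 4; 3,000 runs each) gave 6% to 19% for the Cox test and 6% to 16% for a median-split log-rank test. The median split is an assumption, since 11.1 does not say how a continuous parameter would be grouped.

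**Timing.** This part needs no simulation. Section 3.0 allows a scan after treatment has begun, section 9.0 starts follow-up at the scan, and 11.1 compares the scan's parameters with the treatment effect. Nothing in the three sections keeps post-treatment scans out of that comparison.

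**The case against.** The strongest reply is that the text is silent and does not prescribe a wrong analysis. A Cox model can carry covariates, treatment dates and stage are collected, and recruiting women referred for treatment suggests that many scans will precede it. This stands in part. A reader might infer that the plan rules out adjustment, or that scans will in fact be taken during or after treatment. The documents support neither: they leave both open. But none of the collected variables is assigned to a model, referral for treatment does not mean untreated disease, and with roughly 11 to 16 events per sequence, adjustment chosen after seeing the data is a poor substitute for one stratum fixed in advance.

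A second reply is that the inflation is often small. This stands: at HR 2, or with a 0.4 SD shift, it is between nothing and about three points, and 13 of 27 recurrent is close to the least favourable split. A reader might take 0.78 SD as the plan's own primary-versus-recurrent difference, or conclude that the test always exceeds 5%. Neither is supported.

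Third, an unadjusted test that rejects because the parameter marks a poor-prognosis group is not wrong about the marginal association. It misleads only if the aim is prognostic value beyond disease status, which the plan does not spell out. Nor does the plan set a significance level for this analysis; the 5% in 11.2 belongs to the T2 comparison. The 5% used here is therefore a conventional reference.

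Finally, this is a secondary analysis in a self-described pilot. That limits the weight of the point but does not remove it, because prognostic value is a stated objective with formal tests attached.

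**Conclusion.** The concern holds as a conditional one. Followed as written, 11.1 lets disease status confound the outcome analysis and lets post-treatment scans act as predictors of treatment effect. Under the assumed values the unstratified Cox test rejects in about 5% to 16% of studies for a parameter with no effect within disease status: negligible at the low end and about two to three times nominal at the high end. These figures depend on a recurrent share, hazards and parameter shift that the documents do not give, and they cover confounding only. The timing problem follows from the text itself, but its extent depends on how many scans fall after treatment starts, which is unknown. It would be too strong to infer that the study's main result is compromised: image quality and the tissue comparisons do not depend on this analysis. The change is worth making before the outcome data are analysed.

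**What to change.** In section 11.1:

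1. Add primary versus recurrent status at the scan as a named variable.
2. Stratify the log-rank test and the Cox model by that variable.
3. Limit the treatment-effect and outcome comparisons to scans taken before the start of the treatment being assessed, using the treatment dates already collected. Keep all scans for image quality and tissue comparisons.
4. State that tumour type and stage remain possible confounders, which so few events cannot support adjusting for in full, and that these analyses are exploratory.

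Eligibility does not change. The cost is one added field, some wording, slightly less information in a two-stratum model, and the loss of an unknown number of scans from an already small outcome analysis. That last cost is real. With 12 events, power for a true median-split hazard ratio of 2 is Φ(√(12 × 0.25) × ln 2 − 1.96) = Φ(−0.76) ≈ 22%, and 80% power would need 66 events. The analysis cannot be confirmatory with or without the change, so giving up a little precision for an interpretable estimate is a reasonable exchange.

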11.2 Power analysis

The sample size calculation is exploratory in nature since no protocols with MRF or QTI in gynecological imaging have been published. One prior publication reports the range of traditional T2 relaxation values in one patient with endometrial cancer [15]. Based on the average value of 78 ms T2 relaxation time in endometrial cancer, and on the assumption of 5% difference to other histologies and SD of 5 ms, the calculated targeted sample size is 27 patients per group with power set at 80% and type I error rate of 5% (www.sample-size.net/sample-size-means/).

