9.0 Procedures Involved*

The eligibility of participants with gynecologic cancer will be evaluated by the treating gynecologic surgeon or oncologist during the routine standard of care practice at

The Value of Advanced MR Imaging in Gynecological Tumors and Benign Uterine Fibroids

BWH/DFCI. If a participant meets the inclusion criteria, she will be informed about the study both orally and in paper by handing out the informed consent form. If the subject is willing to participate in the study, her signature to the consent form is obtained by the treating physician at the end of the appointment. In case the participant requests time for reflection, the consent signature can be obtained just prior to MRI by the research coordinator.

The eligibility of control participants with benign fibroid(s) is evaluated by the treating interventional radiologist based on the referral and a phone call made to the participant to give information about the study (Phone Script in Appendix B). Upon eligibility, informed consent will be sent by email or mail. Signature to the consent form will be obtained by a research coordinator prior to the MRI scan.

If the subject is willing to participate in the study, the advanced MRI sequence (either QTI or MRF) will be run along with the routine standard of care MRI. If the subject wishes not to participate, only standard of care MRI sequences will be performed according to the routine protocol.

Institutions will register eligible participants in the Clinical Trials Management System (CTMS) OnCore as required by DF/HCC SOP REGIST-101. When required by REGIST-101, registration must occur prior to the initiation of protocol-specific procedures or assessments.

Routine clinical standard of care pelvic MRI will be performed using a clinical 3T MRI scanner at BWH. The advanced MRI sequence (MRF or QTI) will be supplementary and included along with the current clinical exam. No invasive procedures are needed for MRF or QTI. No extra hospital visit is required related to this study. The duration of routine clinical pelvic MR exam is approximately 30–45 minutes. Running MRF or QTI along with the routine clinical protocol will add this scanning time by approximately 10–15 minutes. There are no reported toxicities related to MRI itself when all the safety guidelines are being followed. No intravenous contrast agent is needed for the advanced MR

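### Section 11.2 does not say which histologies its 27 per group compares, and Section 23 uses 27 as the total of all malignancies per sequence: a two-group T2 contrast of 3.9 ms between histologies then has at most about 50% power, and the 80% does not extend to QTI

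*Combined protocol and SAP*

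**What the plan says.** Section 11.2 sizes the study on one parameter, T2: "Based on the average value of 78 ms T2 relaxation time in endometrial cancer, and on the assumption of 5% difference to other histologies". Taking 5 ms as the SD, it reports this result: "calculated targeted sample size is 27 patients per group with power set at 80% and type I error rate of 5" percent. The 78 ms comes from a published report of conventional T2 values in one patient. The section opens with a caveat: "The sample size calculation is exploratory in nature since no protocols with MRF or QTI in gynecological imaging have been published".

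Section 23 carries the number forward: "Based on sample size calculation (see Section 11.2 Power Analysis), following number of participants will be included in this research study". It lists four groups of 27, which are malignancy and fibroid for MRF and the same pair for QTI, among them "MRF for participants with gynecologic malignancy; n=27" and "QTI for participants with gynecologic malignancy; n=27".

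Section 3 admits to the malignancy group any "primary or recurrent gynecological cancer including uterine endometrial, cervical, vaginal, vulvar, ovarian, and smooth-muscle tumors". That is an open list naming six tumor types, and no quota by type is set.

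Section 11.1 places two kinds of parameter comparison under the primary endpoint, tumor against normal tissue and tumor histologies against one another, for MRF (T1, T2) and for five QTI parameters. The test it names is a one-way analysis of variance across malignant tumors, fibroids and normal tissue.

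Under Section 9, "the advanced MRI sequence (either QTI or MRF) will be run along with the routine standard of care MRI", and Section 19 places the two sequences on different scanners.

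**The concern.** The calculation needs 27 in each of two groups, and the section does not say which groups they are. Endometrial cancer is one of several types inside the malignancy group. If it is to be compared with other malignant types, 27 is needed on each side, yet Section 23 provides 27 malignancies in all. QTI participants cannot make up the difference, because T2 is an MRF parameter and each participant receives one sequence. The QTI groups are also set at 27 on the strength of a calculation that contains no QTI quantity.

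What is at stake is the reading of the results. The plan does not say how a null finding between histologies would be interpreted. A reader relying on the stated 80% could take it as evidence against a 5% difference that a two-group comparison of this size would miss about half the time, even with the most favourable case mix.

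**Working it through.** **Inputs.** Section 11.2 gives a mean of 78 ms, a difference of 5%, an SD of 5 ms, power of 80% and type I error of 5%. Section 23 gives 27 malignancies and 27 fibroids per sequence. Sidedness is not stated. I take the test as two-sided because that reproduces the plan's figure (one-sided gives 21 per group by normal approximation). I also assume a common SD and one T2 value per participant.

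**Effect size.** 0.05 × 78 = 3.9 ms, so d = 3.9/5 = 0.78.

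**The plan's own figure.** By normal approximation, n = 2 × (1.960 + 0.842)² / 0.78² = 25.8, rounded up to 26. For the t-test, power comes from the noncentral t distribution with noncentrality d/√(1/n₁ + 1/n₂) and n₁ + n₂ − 2 degrees of freedom:

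- 26 vs 26: 78.8%
- 27 vs 27: noncentrality 0.78/√(2/27) = 2.866, power 80.3%

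So 27 is the correct t-test answer to the question as posed.

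**The same contrast inside 27 MRF malignancies.** All two-group splits from 2/25 to 13/14 were checked. A selection:

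| Split | t-test | Normal approximation |
|---|---|---|
| 13 vs 14 | 49.5% | 52.6% |
| 9 vs 18 | 45.1% | 48.0% |
| 6 vs 21 | 36.7% | 39.2% |
| 3 vs 24 | 23.2% | 24.6% |

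The maximum is at 13 vs 14, where the noncentrality is 0.78/√(1/13 + 1/14) = 2.025. The plan gives no case mix, so only the maximum is used below.

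**Difference detectable with 80% power at 13 vs 14.** By t-test, d = 1.123, and 1.123 × 5 = 5.6 ms, or 5.6/78 = 7.2%. By normal approximation, (1.960 + 0.842) × 5 × √(1/13 + 1/14) = 5.4 ms, or 6.9%. The plan assumes 3.9 ms (5%).

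**Malignancies needed for the sized contrast.** An even split by t-test gives 79.5% at 53 in total and 80.3% at 54. The plan has 27 on MRF.

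**Which reading the text favours.** The secondary objective in Section 1 lists fibroids and tumor histology as separate comparators, and Section 11.1 speaks of differing tumor histologies. Both point to other malignant types. Against that, the primary objective refers to tumor entities more broadly, and the analysis of variance in Section 11.1 pools the malignancies against fibroids, which fits the groups in Section 23. The text leans to the first reading without settling it.

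**If fibroids are the comparator.** 27 vs 27 on MRF T2 has 80.3% power, provided that the 3.9 ms (5% of an endometrial-cancer mean) and the 5 ms SD carry over to a mixed malignancy group against fibroids. The table above still applies to a two-group comparison between histologies.

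**QTI.** Section 11.1 names five QTI parameters. The documents give no mean, SD or difference for any of them, so power cannot be computed.

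**The case against.** The strongest reply is that the plan already declares its calculation exploratory, names T2 as its only input, and calls the study a pilot in Section 15. On the fibroid reading, Section 23's groups match the analysis of variance in Section 11.1, and nothing contradicts. Section 11.2 never expressly claims power for the histology comparison. This limits the seriousness of the point. It does not resolve it, because the exploratory label explains why the inputs are uncertain and not which contrast the 80% describes. Section 23 then uses the number for every group without the caveat.

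Four stronger conclusions are tempting, and the documents do not support them:

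- *No histology comparison can exceed about 50% power.* The ceiling is for a two-group contrast of exactly 3.9 ms. With three types of 9 each, two of them lying 5% either side of the third, the noncentrality is 9 × (3.9² + 3.9²)/25 = 10.95, and a three-group analysis of variance has 80.0% power. Section 11.2 neither states nor excludes that pattern.
- *Only one MRF T2 comparison can reach 80%.* With 27 tumor–normal pairs at the same 3.9 ms and 5 ms, a paired t-test has about 79% power at an assumed correlation of 0, 83% at 0.1 and 91% at 0.3. Not every participant need have every normal structure.
- *QTI is underpowered.* Its power is unknown, and all that follows is that the T2 figure does not supply it.
- *There is no T2 evidence on fibroids to plan from.* The documents are silent on whether such values exist.

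**Conclusion.** The point holds, as a correction to the power statement. The arithmetic behind 27 is right, but the groups it was computed for are undefined, and the number is then applied to different groups and to a different technique. On the reading that the text favours, the sized contrast has at most 49.5% power (52.6% by normal approximation) where 80% is stated. On the other reading the 80% stands for malignancy versus fibroid on MRF T2, and a two-group 3.9 ms contrast between histologies, listed under the primary endpoint, has that same ceiling. On neither reading does the 80% apply to QTI.

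These figures rest on the plan's own assumed 3.9 ms and 5 ms, a two-sided 5% test and the most favourable split. A larger true difference would raise the power; a larger SD or a less even case mix would lower it. The design of a pilot study is not threatened, but the statement should be corrected before the results are read against it.

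**What to change.** **Section 11.2.** The sponsor, who alone knows which contrast was intended, should name it. Suggested wording to follow: *The 80% applies only to a two-sided, two-sample comparison of MRF T2 with 27 vs 27, at a difference of 3.9 ms and an SD of 5 ms, both assumed values. A two-group contrast of 3.9 ms between histologies within the 27 MRF malignancies has at most about 50% power (t-test, 13 vs 14). No power is claimed for QTI parameters.*

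**Section 23.** Add: *The 27 in the QTI groups is carried over from the MRF T2 calculation and has no QTI power basis.*

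**Section 11.1.** Add: *Comparisons between tumor histologies are reported as estimates with 95% confidence intervals; a null result is not read as absence of a 5% difference.*

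The cost is a less favourable power statement and an explicit limit on how a comparison listed under the primary endpoint may be interpreted. No participants, procedures or tests are added.
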